11.5. Exploratory Endpoints

11.5.1. Week 1

Assessment of change in VEINES-QOL/Sym (Questions 1 through 8) at post treatment follow-up visit at Week 1 as compared to Baseline

11.5.2. Week 6

Assessment of change in VEINES-QOL/Sym (Questions 1 through 8) at Week 6 post treatment follow-up visit as compared to Baseline

11.5.3. Week 12

Assessment of change in VEINES-QOL/Sym (Question 1, excluding HASTI, through Question 8) at Week 12 post treatment follow-up visit as compared to Baseline

11.6. Determination of Sample Size

The sample size of 50 patients (25 patients per treatment group) is based on both efficacy and safety considerations. The primary endpoint is change from baseline in the weekly average symptom score of a subset of the VEINES-QOL/Sym questionnaire (based on HASTI symptoms from Question 1: Heaviness, Achiness, Swelling, Throbbing, Itching) at Week 12 for both treatment groups combined.

Assuming a true mean change from baseline to 12 weeks of -5.44 and a standard deviation of 3.52 for the change from baseline, a sample size of 50 would provide at least 99% power to reject the null hypothesis that the mean change from baseline equals 0, based on a one-sample t-test with a 0.050 two-sided significance level. A sample size of 25 (that is, by treatment group) would also provide at least 99% power to reject the null hypothesis that the mean change from baseline equals 0.

11.7. Analysis of Primary Efficacy Endpoint

The null hypothesis is that the mean change from baseline for the primary efficacy endpoint equals 0. The alternative hypothesis is that the mean change does not equal 0.

The primary analysis will be a one-sample t-test for both treatment groups combined, to test the null hypothesis that the mean change from baseline equals 0.

To evaluate a dose-response relationship, two analyses will be performed. First, the primary analysis will be performed for each treatment group separately. Second, an analysis of covariance (ANCOVA) will be performed to compare the change from baseline for STS 1% versus STS 3% with treatment as a class variable and with the baseline weekly average HASTI symptom score as a covariate in the model.

Missing data for the Week 12 weekly average HASTI symptom score will be imputed using the last observation carried forward (LOCF) method.

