11. PLANNED STATISTICAL METHODS FOR ASSESSMENT OF EFFICACY AND SAFETY

11.1. General Considerations

Continuous variables will be summarized using descriptive statistics, specifically the mean, median, standard deviation, minimum and maximum. Categorical variables will be summarized using frequencies and percentages. All statistical tests will be performed at the 0.05 significance level (p -value ≤ 0.050) unless otherwise indicated.

For efficacy analyses, missing post-treatment data will be imputed using last observation carried forward (LOCF). Missing safety data will not be imputed.

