11.8. Analysis of Other Efficacy Endpoints

The primary analysis for each endpoint will use LOCF methodology for the imputation of missing data.

Continuous endpoints will be summarized using descriptive statistics and will be analyzed using a one-sample t-test to test the null hypothesis that the mean change from baseline equals 0.

The secondary efficacy endpoint, the elimination of saphenous vein reflux at Week 12 post-treatment, will be summarized for both treatments combined using the count and percentage, together with a 95% Wilson (score) confidence interval for the proportion.

To evaluate a dose-response relationship, two analyses will be performed for each endpoint. First, the analyses performed for both treatments combined will be repeated for each treatment group separately. Secondly, for continuous endpoints, an ANCOVA will be performed to compare the change from baseline for STS 1% versus STS 3% with treatment as the class variable and with baseline score as the covariate. For vein closure rate, the treatment difference for STS 1% versus STS 3% for the proportion will be assessed by a chi-square test together with a 95% Wilson (score) confidence interval for the treatment difference.

For each continuous endpoint, the change from baseline to each scheduled visit will be analyzed in the same manner as the Week 12 assessment. Both LOCF and observed cases analyses will be performed.

The correlation between Week 12 efficacy endpoints will be explored using a Spearman correlation coefficient for pairs of quantitative variables, and Kendal's tau for the correlation of the elimination of saphenous vein reflux (yes, no) with quantitative variables.

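### Do the per-arm tests against zero, listed as dose-response analyses, leave the plan without a sound comparison of STS 1% and 3%?

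*Combined protocol and SAP*

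**What the plan says.** Section 11.7 defines the primary analysis as a one-sample t-test of mean change in the weekly average HASTI score against 0, both arms pooled. It then continues: "To evaluate a dose-response relationship, two analyses will be performed. First, the primary analysis will be performed for each treatment group separately". The second of the two analyses is an ANCOVA of change from baseline, STS 1% against STS 3%, with treatment as a class variable and the baseline HASTI score as covariate.

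Section 11.8 carries the arrangement over to the other endpoints: "First, the analyses performed for both treatments combined will be repeated for each treatment group separately". For continuous endpoints an ANCOVA of 1% against 3% again follows. For vein closure the difference between arms "will be assessed by a chi-square test together with a 95% Wilson (score) confidence interval for the treatment difference". Section 11.8 adds: "For each continuous endpoint, the change from baseline to each scheduled visit will be analyzed in the same manner as the Week 12 assessment".

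On reporting, 11.1 says: "Continuous variables will be summarized using descriptive statistics, specifically the mean, median, standard deviation, minimum and maximum". It does not mention confidence intervals. On power, 11.6 says of the per-arm test: "A sample size of 25 (that is, by treatment group) would also provide at least 99% power to reject the null hypothesis". That null hypothesis is a mean change of 0.

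**The concern.** A test of change against 0 within one arm asks whether patients on that concentration improved. It does not ask whether they improved more or less than patients on the other. Listing it as one of two dose-response analyses invites two misreadings:

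- Two significant arms may be taken to show that the doses are equivalent.
- One significant and one non-significant arm may be taken to show that they differ.

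The second is the familiar error of treating the difference between significant and not significant as itself significant. Because 11.8 repeats the pattern across endpoints and visits, the label would recur in many tables. The plan also names a 95% interval for the vein closure difference but none for the ANCOVA difference, and the per-arm power of at least 99% in 11.6 could be mistaken for power to tell the doses apart. If the dose conclusion rested on the per-arm p-values, it would rest on nothing that compares the doses.

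**Working it through.** **Inputs.** All are from 11.6: mean change −5.44 (written below as an improvement of 5.44), SD of change 3.52, 25 per arm and 50 in total, test "based on a one-sample t-test with a 0.050 two-sided significance level". The documents give no assumed difference between the arms and no correlation between baseline and change. The arm-specific means below are therefore assumptions, and an unadjusted two-sample t-test stands in for the ANCOVA. Adjustment would be expected to narrow the interval to the extent that baseline predicts change.

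**Step 1: the plan's own power.** The noncentrality is (5.44 / 3.52) × √n.

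- n = 50: 1.5455 × 7.0711 = 10.93, power above 99.9999%.
- n = 25: 1.5455 × 5 = 7.73, power above 99.9999%.

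The stated figure of at least 99% is correct for both. It refers to change from 0.

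**Step 2: what the per-arm tests say about dose.** The chance that both arms are significant is the product of the two one-sample powers. The two-sample noncentrality is the difference divided by 3.52 × √(2/25) = 0.9956, with 48 degrees of freedom.

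| Assumed improvement, two arms | Both per-arm tests significant | Two-sample test rejects |
|---|---|---|
| 5.44 and 5.44 | over 99.99% | 5% |
| 4.44 and 6.44 (difference 2) | over 99.9% | 50% |
| 3.94 and 6.94 (difference 3) | 99.97% | 84% |
| 3.63 and 7.25 (one arm half the other) | about 99.9% | about 95% |
| 3.44 and 7.44 (difference 4) | 99.7% | 98% |

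Every row averages 5.44, the plan's pooled change. In the fourth row the arms are 5.44 × 2/3 and 5.44 × 4/3, and the noncentrality is 3.62 / 0.9956 = 3.64. The per-arm result is nearly constant while the direct comparison moves with the difference.

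**Step 3: how often equal doses would give a split result.** With equal arms and per-arm power p, exactly one is significant with probability 2p(1 − p).

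| Common improvement | p | 2p(1 − p) |
|---|---|---|
| 2.0 | 0.778 | 35% |
| 2.5 | 0.926 | 14% |
| 3.0 | 0.983 | 3% |
| 3.5 | 0.997 | 0.5% |
| 5.44 | over 0.9999 | effectively nil |

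A misleading split needs a true change well below the planned one: 2.0 / 5.44 is 37% of it, and 3.0 / 5.44 is 55%.

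**Step 4: precision of the comparison that addresses dose.** The unadjusted 95% half-width is t(0.975, 48) × 0.9956 = 2.011 × 0.9956 = 2.0 points. A difference of about 2.85 points has 80% power.

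**Step 5: what the plan does with the per-arm results.** The text of 11.7 and 11.8 contains no decision rule based on them. The objectives in the synopsis and the endpoints in Table 1 are all changes from baseline or reflux status at follow-up. None is a comparison of the two concentrations, and no dose-selection rule is stated.

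**The case for a change.** The strongest case for a change is that the text assigns the per-arm tests a purpose they cannot serve, that a valid second analysis does not turn the first into dose-response evidence, and that the repair costs only a few words plus an interval from a model already planned. In a two-dose pilot the difference between arms and its precision matter, and pre-specifying an interval is firmer than relying on software output.

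Part of this stands. A within-arm test or interval holds no 1% against 3% contrast, and the figures above confirm that it is uninformative about dose at the planned effect. The rest does not require action:

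- The two analyses are specified together and read naturally as a package: each dose's own result, then the contrast. Whether each dose shows improvement is a legitimate question.
- What 11.8 repeats by arm includes descriptive statistics. Side-by-side mean changes and SDs are an ordinary part of describing a dose comparison.
- The interval for an ANCOVA treatment difference is routine output. The description of summary statistics in 11.1 does not exclude it, and 11.7 names no interval for the pooled primary change either. This is the plan's general level of detail.
- The looseness is not confined to continuous endpoints. The per-arm Wilson intervals for reflux elimination sit under the same label and are equally harmless, because the chi-square comparison accompanies the closure analysis.

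**Conclusion.** No change is needed. The label on the per-arm analyses is imprecise, but the plan already contains the analysis that answers the dose question, and an analyst following it as written would base the dose conclusion on the ANCOVA (or, for closure, the chi-square test and its interval). Relabelling would change no estimate, p-value or decision. A split result that misleads is effectively nil at the planned change of 5.44 and reaches 35% only if both arms truly improve by about 2.0. Even then the ANCOVA is there to show whether the arms differ.

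This rests on the plan's SD of 3.52, full enrolment of 25 per arm, assumed arm means (the documents give none), and an unadjusted test in place of the ANCOVA. It also assumes that the report gives the ANCOVA difference with its interval, as is usual. A reader should note that the per-arm power in 11.6 concerns change from 0, and that the comparison between doses is much less precise, at about ±2.0 points unadjusted.

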11.8. Analysis of Other Efficacy Endpoints

The primary analysis for each endpoint will use LOCF methodology for the imputation of missing data.

Continuous endpoints will be summarized using descriptive statistics and will be analyzed using a one-sample t-test to test the null hypothesis that the mean change from baseline equals 0.

The secondary efficacy endpoint, the elimination of saphenous vein reflux at Week 12 post-treatment, will be summarized for both treatments combined using the count and percentage, together with a 95% Wilson (score) confidence interval for the proportion.

To evaluate a dose-response relationship, two analyses will be performed for each endpoint. First, the analyses performed for both treatments combined will be repeated for each treatment group separately. Secondly, for continuous endpoints, an ANCOVA will be performed to compare the change from baseline for STS 1% versus STS 3% with treatment as the class variable and with baseline score as the covariate. For vein closure rate, the treatment difference for STS 1% versus STS 3% for the proportion will be assessed by a chi-square test together with a 95% Wilson (score) confidence interval for the treatment difference.

For each continuous endpoint, the change from baseline to each scheduled visit will be analyzed in the same manner as the Week 12 assessment. Both LOCF and observed cases analyses will be performed.

The correlation between Week 12 efficacy endpoints will be explored using a Spearman correlation coefficient for pairs of quantitative variables, and Kendal's tau for the correlation of the elimination of saphenous vein reflux (yes, no) with quantitative variables.

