The study data will be analyzed and reported based on all patients' data from baseline up to the time when all patients have completed the Week 12 post-treatment follow-up visit or have discontinued from the study. If a patient has discontinued from the study, the Last Observation will be carried forward (LOCF) for analysis.

LIST OF ABBREVIATIONS AND TERMS

List of Abbreviations

Abbreviation	Term
AE	Adverse Event
ASV	Accessory Saphenous Vein
CEAP	Clinical-Etiology-Anatomy-Pathophysiology Classification
DICOM	Digital Imaging and Communications in Medicine
DVT	Deep Venous Thrombosis
EO	Ethylene Oxide
EQ-5D-5L	European Quality of Life - 5 Dimensions
FDA	Food and Drug Administration (United States of America)
GCP	Good Clinical Practice
GSV	Great Saphenous Vein
HASTI	Heaviness, Achiness, Swelling, Throbbing, Itching
IC	Intravascular Coagulation
IRB	Institutional Review Board
MDU	Motor Drive Unit
PASTE	Post-Ablation Superficial Thrombus Extension
PE	Pulmonary Embolism
rVCSS	Revised Venous Clinical Severity Score
SAE	Serious Adverse Event
SFJ	Sapheno-Femoral Junction or Saphenofemoral Junction
SSV	Small Saphenous Vein
STS	Sodium Tetradecyl Sulfate
SVS	Saphenous Vein Segment
TS	Treatment Section
US	United States
VAS	Visual Analog Scale
VEINES-QOL/SYM	Venous Insufficiency Epidemiological and Economic Study-Quality of Life Questionnaire
VI	Vascular Insights, LLC

List of Terms and Definitions

Term	Definition
Adverse Event	An adverse event (AE) is any untoward medical occurrence in a patient or clinical investigation subject administered a study product. The occurrence, which may or may not have a causal relationship with the investigational treatment, may include any clinical or laboratory change that does not commonly occur in that patient and is considered clinically significant.
Baseline	Establishment of patient eligibility for study treatment at least 7 days prior to Treatment visit (Visit 2)
CEAP Classification	The CEAP classification is a method for evaluating venous disease of the leg based on clinical , etiologic , anatomic , and pathophysiologic data.
CRO	Clinical Research Organization, which may be assigned responsibility to perform selected function of the study
Day-of-Treatment	The day on which the single-treatment procedure is performed— the treatment begins and ends on the same day (Visit 3)

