End-of-Study for Patient	The end of study for a patient is when the patient has completed the required post-treatment study visits or has discontinued from the study.
Enrolled Patient	Individual who has signed the Informed Consent Form.
Elimination of Saphenous Vein Reflux	Vein closure and/or vein competence of the treatment section (TS) of the selected saphenous vein, as demonstrated by duplex ultrasound at Week 12 post treatment (Visit 6)
Follow-up Period	From the day following Day of Treatment (Visit 3) to completion of the Week 1, 6 and 12 (Visits 4, 5 and 6) post-treatment follow-up visits
HASTI	H eaviness, A chiness, S welling, T hrobbing, I tching symptom from VEINES-QOL/Sym questionnaire
Institutional Review Board (IRB)	A type of committee used in research in the United States that has been formally designated to approve, monitor, and review biomedical and behavioral research involving humans
Regulatory Agency	USA Food and Drug Administration (FDA)
Saphenous Vein Segment	A segment of saphenous vein with no deep venous junction
Screening Period	After reviewing and signing the Informed Consent Form (ICF) for participation in the study, an individual will be screened for eligibility to participate in study during Screening (Visit 1), Baseline (Visit 2), Day of Treatment (Visit 3).
Sponsor	Vascular Insights, LLC

Term	Definition
Start-of-Study	Study starts when first patient signs the ICF (Visit 1).
Study Drug	Sodium Tetradecyl Sulfate (STS) 1% and 3%
Study Drug Delivery System	ClariVein infusion catheter system
Study Product	ClariVein RES (Sodium Tetradecyl Sulfate delivered via the ClariVein infusion catheter system)
VICARES Clinical Study Procedure Manual	A manual provided to the Investigational Sites that include instruction for device operation, study drug and delivery device preparation, and ultrasound assessments for the ClariVein RES.
Study Treatment	The study treatment, is the endovenous administration of either 1% or 3% STS delivered intravenously via the ClariVein, with a maximum STS volume of 10 mL per single treatment procedure.
Suspected Adverse Event	Any adverse event (AE) for which there is a reasonable possibility that the study product caused the AE. For the purposes of IND safety reporting, "reasonable possibility" means there is evidence to suggest a causal relationship between the investigational product and the AE.

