11.10. Protocol Deviations/Violations

Protocol deviations will be identified prior to database lock and will be listed by treatment group in the clinical study report. A protocol violation occurs when the patient, Investigator, or Sponsor fails to adhere to significant protocol requirements affecting the inclusion/exclusion criteria, patient safety, or primary endpoint criteria.

Protocol violations for this study include, but are not limited to, the following:

- Failure to meet inclusion/exclusion criteria
- Use of a prohibited concomitant medication
- Failure to attend two post treatment visits: of which one is Week 12

Failure to comply with Good Clinical Practice (GCP) guidelines will result in a protocol violation. Sponsor will determine if a protocol violation will result in withdrawal of a patient from the study.

When a protocol violation occurs, it will be discussed with the Investigator and a Protocol Violation Form detailing the violation will be generated. This form will be signed by a Sponsor representative and the Investigator. A copy of the form will be filed in the site's regulatory binder and in the Sponsor's files.

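### LOCF, with no limit on how early the carried value is, is the primary rule for every efficacy endpoint, and the observed-cases check omits reflux and reaches primary HASTI only on a generous reading

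*Combined protocol and SAP*

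**What the plan says.** LOCF is set out in four places.

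- Synopsis, Data Analysis: "If a patient has discontinued from the study, the Last Observation will be carried forward (LOCF) for analysis".
- Section 11.1 applies LOCF to missing post-treatment data in efficacy analyses generally.
- Section 11.7, on the primary endpoint: "Missing data for the Week 12 weekly average HASTI symptom score will be imputed using the last observation carried forward (LOCF) method".
- Section 11.8, on the other endpoints: "The primary analysis for each endpoint will use LOCF methodology for the imputation of missing data".

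No section restricts the visit from which a value may be carried. Post-treatment HASTI diaries cover the 7 days after treatment and the 7 days before the Week 6 and Week 12 visits (Section 8.2.3). Ultrasound is done at Weeks 1, 6 and 12 (Table 3). One post-treatment assessment of the primary variable, with a baseline, admits a patient to the MITT population (Section 11.2.2).

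Observed cases appears once, in Section 11.8: "Both LOCF and observed cases analyses will be performed". The sentence before it reads: "For each continuous endpoint, the change from baseline to each scheduled visit will be analyzed in the same manner as the Week 12 assessment".

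Section 11.10 lists as a protocol violation: "Failure to attend two post treatment visits: of which one is Week 12".

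**The concern.** The List of Terms and Section 8.2.2 define elimination of reflux at Week 12. A scan carried from Week 1 or Week 6 does not observe that. It assumes that a vein closed early stays closed, or that one still refluxing stays so.

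For HASTI, the stocking is worn for 72 hours and then in the daytime for 2 weeks (Section 7.5.2). The Week 1 diary therefore falls wholly within the compression period and the Week 12 diary does not. Carrying one to the other mixes two conditions of measurement.

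The check that would show how much this matters is incomplete. Reflux is binary, so a sentence that follows on from continuous endpoints does not reach it. Primary HASTI is continuous, but its own section names only LOCF, and the observed-cases sentence sits in the section on other endpoints.

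At stake are the size of the HASTI change, the Week 12 reflux rate and the 1% versus 3% contrast. For a Phase 2 pilot whose primary test is almost certain to reject, these estimates are much of what the trial will teach.

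**Working it through.** **1. The plan's own figure.** Section 11.6 gives a mean change of -5.44, SD 3.52, two-sided alpha 0.05 and power of at least 99% at n=50 and n=25. The noncentrality is (5.44/3.52)×√n, which is 7.73 at n=25 and 10.93 at n=50. Power exceeds 99.99% at both sizes, so the stated figure reproduces.

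**2. Stress on the primary test.** Set 30% of patients to zero change.

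- Mean = 0.7×(-5.44) = -3.81
- SD = √(0.7×3.52² + 0.3×0.7×5.44²) = √(8.67 + 6.21) = 3.86
- Power is above 99.9% at n=50 and 99.7% at n=25.

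**3. Reflux, pooled.** The documents give no dropout, closure or reopening rate. Assume 50 treated patients, m without a Week 12 scan, and 85% elimination among those scanned. Let the carried rate pc be 98, 90, 85 or 70%, and the true Week 12 rate in the missing pt be 85, 70 or 50% (12 combinations).

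- LOCF bias = (m/50)(pc - pt)
- Observed-cases bias = (m/50)(0.85 - pt)
- Missing counted as not eliminated: bias = -(m/50)pt

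| Missing | LOCF (points) | Observed cases | Missing = not eliminated |
|---|---|---|---|
| 3 | -0.9 to +2.9 | 0 to +2.1 | -5.1 to -3.0 |
| 5 | -1.5 to +4.8 | 0 to +3.5 | -8.5 to -5.0 |
| 10 | -3.0 to +9.6 | 0 to +7.0 | -17.0 to -10.0 |

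Observed cases is closer to the truth than LOCF in 7 combinations, equal in 3 and further away in 2 (carried rate 70% with true rate 70% or 50%). Three of the 7 come from setting pt to 85%, where observed cases has no bias by construction. Without those settings the count is 4 closer, 2 equal and 2 further away.

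**4. Reflux, one worked case.** Five scans are missing, all five last scans showed elimination, and 38 of 45 observed patients are successes. Wilson 95% intervals:

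- LOCF: 43/50 = 86.0% (73.8 to 93.0), width 19.2 points
- Observed cases: 38/45 = 84.4% (71.2 to 92.3), width 21.0 points
- Missing = not eliminated: 38/50 = 76.0% (62.6 to 85.7)

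**5. Reflux, by arm.** With 0 versus 5 of 25 missing, bias in the contrast is 0.2×(pc - pt) = -3.0 to +9.6 points for LOCF and 0.2×(0.85 - pt) = 0 to +7.0 for observed cases. The standard error is √(2×0.85×0.15/25) = 10.1 points.

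**6. HASTI, random dropout.** If 9% drop out after Week 1 and 9% after Week 6, LOCF bias = 0.09×(Week 1 mean - Week 12 mean) + 0.09×(Week 6 mean - Week 12 mean). The Week 12 mean is -5.44.

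- Assumed early means -2.72 and -4.50: 0.09×2.72 + 0.09×0.94 = +0.33
- Assumed early means -6.80 and -6.00: 0.09×(-1.36) + 0.09×(-0.56) = -0.17

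So LOCF is biased even when dropout is unrelated to outcome, unless the early means equal the Week 12 mean.

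**7. HASTI, simulation.** Assumptions: n=50; SD 3.52 at each visit; between-visit correlation 0.4 or 0.7; the two early profiles above and a flat one; dropout either random or more likely with a worse last observed score; 18-19% missing at Week 12. Bias in the mean change (positive means less improvement than the truth):

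- LOCF: -0.20 to +0.68
- Observed cases: -0.44 to +0.01
- Repeated-measures likelihood: -0.01 to +0.01

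The standard error of the arm difference is 3.52×√(2/25) = 1.00.

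**The case against.** LOCF is pre-specified and consistent across four sections, in a 50-patient pilot where reflux has no success threshold and the dose comparison is exploratory. In the simulation LOCF mostly understates HASTI benefit, while observed cases leans towards overstating it. This stands, and it limits the point to the quality of the estimates.

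The plan also has safeguards. Section 7.7.1 asks for a visit within 14 days of a decision to discontinue, and Section 9.2 for at least two documented attempts to obtain an early discontinuation visit. Some withdrawn patients stay in follow-up to Week 12. Section 11.10 flags a patient who misses Week 12 and another visit. These reduce the problem, but the assessments at the early visit are not listed, the violation item excludes nobody and does not cover a patient who misses Week 12 alone, and none of them alters the rule.

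The observed-cases sentence names no endpoint, so it could be stretched to HASTI. That reading is possible, but the primary endpoint should not depend on it.

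The repeated-measures result is close to unbiased partly because the simulated dropout was missing at random. No other mechanism was simulated.

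A reader might infer that LOCF inflates efficacy, or that observed cases should replace it as the reflux headline. Neither is supported. LOCF bias runs both ways. Observed cases drops patients whose last scan showed reflux, and in the grid above it errs only upwards. The choice between them is a trade-off.

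**Conclusion.** The point holds as a cheap improvement to the estimates. The rule allows an early value of any age to stand as Week 12, and the planned sensitivity analysis leaves out reflux and leaves primary HASTI in doubt.

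A reader might go further and conclude that the primary result is at risk. It is not: the pooled test keeps power above 99% under a harsher assumption than LOCF itself.

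Under the assumed rates the shifts are modest: a few points on the pooled reflux rate with 5 scans missing, up to 9.6 points on the reflux contrast if all 5 are in one arm (against a standard error of about 10), and up to about 0.7 on the HASTI mean change. If few patients miss Week 12, all of these shrink in proportion. Confidence in the size is limited, because the documents give no dropout or reopening rate. Confidence that the rule and the gap are as described is high.

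**What to change.** 1. **HASTI and other continuous endpoints measured at Weeks 1, 6 and 12.** Estimate the Week 12 change, pooled and by arm, from a baseline-adjusted mixed model for repeated measures on observed data. Test the same null of zero mean change and state the missing-at-random assumption. Keep the planned t-test and ANCOVA, with LOCF and with observed cases, as sensitivity analyses that explicitly include primary HASTI. Note that observed cases can overstate benefit when patients doing worse drop out. CEAP and rVCSS are outside this change, because Table 3 schedules no post-treatment assessment of them before Week 12.
2. **Reflux.** Report side by side, pooled and by arm, the LOCF result, the observed Week 12 result with its denominator, and missing counted as not eliminated, labelled as a lower bound only. Which of the first two is the headline is for the sponsor to choose in advance. No statement about durability at Week 12 should rest on LOCF alone.
3. **Transparency.** Tabulate by arm the number of missing Week 12 values and the visit from which each was carried.

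The cost is SAP wording and modest programming on data already collected. The downsides are reliance on missing at random for the model and a slightly wider observed-cases interval for reflux (21.0 versus 19.2 points in the case with 5 missing).
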